10.3.1 Summary of baseline data and flow of patients

A diagram of participant flow through the trial is presented in Appendix 2.

Baseline demographics and measurements will be summarised using number and percentage for categorical data; while continuous variables will be summarised using mean and standard deviation where data follows normality assumptions or median and interquartile range where normality assumptions are not met. No statistical tests are planned to assess the difference in baseline variables between arms.

The baseline variables that will be summarised include the following:

- Age
- Gender
- Ethnicity
- Medical history
- Physical exam
- Vital signs
- Extended MRC dyspnoea score (eMRC)
- Electrocardiogram (ECG)
- Exploratory blood samples (Trop I, BNP, FBC, serum & plasma)
- Spirometry
- WHO Clinical Progression Score

10.3.2 Primary outcome analysis

The main approach to primary analyses will be intention-to-treat (ITT), where the ITT population consist of all randomised participants. The primary analysis will fit the Cox proportional hazard model for the primary outcome of the time to re-hospitalisation or death (any cause) as the dependent variable, treatment group as an explanatory factor and baseline MRC dyspnoea score (≤ 3 , > 3) and past hospitalisation in the previous 12 months ($(0, \geq 1)$) (Stratification factors). This analysis will be accompanied by Kaplan-Meier survival curves alongside with log rank test to compare the survival rate between the two groups. A hazard ratio (HR) of the mepolizumab relative to placebo, with their associated 95% confidence interval and p-values will be reported. A p-value ≤ 0.05 will be considered as significant difference. Time until event (re-hospitalisation or death from any cause) will be measured in days from randomisation until re-hospitalisation, death or 12-month follow-up assessment, whichever happens first. Participants with no event (no re-hospitalisation or alive) assessed during follow-up visits will be censored at the last assessment date free from event. Participants who do not complete the 12-month follow-up will be included in the primary analysis; those without a recorded event will be censored. Participants who withdraw from the trial will be censored at the date of withdrawal and participants lost to follow up will be censored at the date last assessment.

Proportional hazard assumption for the Cox proportional hazard model will be checked using the statistical tests and graphical diagnostics based on the Schoenfeld residuals.

10.3.3 Secondary outcome analysis

All secondary end-points will be analysed using the ITT population, with the exception of adverse events, for which we will analyse the safety population, consisting of all participants who received at least one dose of trial medication. The count outcomes, number of hospital readmissions and number of moderate exacerbations over 48 weeks, will be analysed using the per protocol (PP) population where patients will be included in the analysis if they have a received a minimum duration of trial treatment of 24 weeks.

All time to event secondary outcomes will be analysed the same way as the primary outcome.

All count secondary outcomes, number of hospital readmissions and number of moderate exacerbations, will be analysed using a negative binomial regression model. If there is no evidence of over-dispersion, a Poisson regression model will be used in place.

All binary secondary outcomes will be compared between treatment groups using logistic regression.

All continuous longitudinal outcomes (repeated measurements) will be compared using mixed effects model with patient as a random effect to account for repeated measures over time. This method will enable handling of missing data within the follow-up visits.

This trial has a single primary outcome, therefore there will not be a formal adjustment for multiple significance testing.

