4.1 Truncated follow-up

Participants randomised from July 2023 to December 2023 will be consented to a truncated follow-up model, whereby the timing of the last participant last visit will remain on the same timeline as originally planned; this will result in participants consented in July to have up to the 44-week follow-up, those in August will have up to the 40-week follow-up, and so on. Participants will be dosed for a minimum of 20 weeks (participants will be dosed at baseline, therefore all participants will receive at least 6 doses), with secondary outcomes measured as per original timelines (baseline, 4 weeks, 8 weeks, etc.) however final outcome measures normally measured at 48 weeks will occur at 4 weeks \pm 7 days post final dosing visit.

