10.7 Participant population

The primary analysis for each efficacy outcome will be by 'intention to treat' analysis; all the participants randomised in to the trial (regardless of whether they received trial drug) will be analysed in their allocated group. Outcome data obtained from all participants will be included in the data analysis. The primary analysis of safety outcomes will be analysed using the safety population. The safety population will be comprised of the all individuals that received at least one injection of either the active dose or the placebo, with individuals that received any injections of the active dose being in the mepolizumab arm.

Some of the secondary outcomes i.e. number of hospital readmissions and number of moderate exacerbations over 48 weeks, will be analysed on the per-protocol population where patients will be included in the analysis if they have a received a minimum duration of trial treatment of 24 weeks.

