4.1.2 Minor deviations

Participants visit/assessment not performed as per protocol

4.2 *Intention-to-treat Population*

The primary analysis for each efficacy outcome will be by ‘intention to treat’ analysis; all the participants randomised into the trial (regardless of whether they received trial drug) will be analysed in their allocated group. Outcome data obtained from all participants will be included in the data analysis.

4.3 *Modified intention-to-treat population*

The modified intention-to-treat will be comprised all the participants randomised to the trial (regardless of whether they received trial drug), analysed in their allocated group, where data is available. Therefore, participants with missing outcome data will be excluded from the analysis (i.e complete case analysis). No imputation will be carried out for the missing data.

4.4 *Per-protocol Population*

The per protocol population will contain all participants randomised who do not reach any of the listed definitions for major protocol deviations. Individuals without a major deviation will be included in the per-protocol population whilst on trial treatment, this is considered to be 4 weeks after the last dose. If a participant dies before ending trial treatment, time is capped by death date.

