6.5 Secondary Outcome Analyses

6.5.1 Primary Analysis of Secondary Outcomes

All secondary outcome (except for AEs and SAEs) will be analysed on the modified intention to treat population. The secondary outcomes of adverse and serious adverse event counts will be analysed on the safety population.

All time to event secondary outcomes will be analysed the same way as the primary outcome.

All count secondary outcomes, number of hospital readmissions and number of moderate exacerbations, will be analysed using a negative binomial regression model. If there is no evidence of over-dispersion, a Poisson regression model will be used in place.

All continuous longitudinal outcomes (repeated measurements) will be compared using mixed effects model with patient as a random effect to account for repeated measures over time. This method will enable handling of missing data within the follow-up visits.

This trial has a single primary outcome, therefore there will not be a formal adjustment for multiple significance testing.

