6.5.1.3 Count Outcomes

A generalised linear model (assuming a negative binomial distribution, which accounts for variability among participants in the number of and frequency of the count variable) will be fitted for each count outcome measure with explanatory variables of treatment arm and stratification variables, and log-time on study as an offset. The offset (log-time), allows for different lengths of follow-up time for each participant (Keene et al, 2008). Time on study will be capped at 49 weeks. This assumes that missing data is missing at random (MAR), and will be applied where all of the available observed data are analysed without deletion nor imputation.

The count data is assumed to follow a negative binomial distribution with the over dispersion. If the dispersion is found to be non-significant (i.e no evidence of over-dispersion) we will consider the simpler Poisson model where the dispersion parameter equals to zero. The ratio of the rates (RR) on the intervention arm relative to placebo, associated two-sided 95% confidence interval (CI) and p-value will be reported. A value of 1.0 would indicate the same rate as placebo; the lower the ratio the greater reduction in exacerbations compared with placebo. A two-sided p-value ≤ 0.05 will be considered

as a significant difference in the number of COPD exacerbations in 48 weeks between the two treatment arms.

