6.5.3 Sensitivity Analyses

The primary analyses for all none time event outcomes (i.e continuous, binary and count outcomes) will consider any missing data to be missing at random (MAR) and complete case analysis carried out. However, if comparison of patterns of missingness and descriptive differences between treatment arms indicate this assumption is not valid, additional sensitivity analyses may be carried out and methods of imputation will be included in detail in the statistical analysis plan.

To ensure the reliability of the analysis of key secondary outcome measures, we will conduct a sensitivity analysis under various scenarios. This will involve evaluating the secondary outcomes; number of readmissions, number of exacerbations, and SGRQ (assessed for three sub-domains and the total score), to thoroughly assess the robustness of our results.

Individuals will be considered to have had some missing data for the two count variables if they have less than 47 weeks (48 weeks – 7day window) follow-up with the exception of those with planned truncated follow-up.

In the first approach, regardless of whether missingness is assumed to be random or non-random, we will perform the outlined statistical procedures. Additionally, we will provide descriptive characteristics of the missing group compared to the non-missing group, exploring potential similarities or dissimilarities between them. This comprehensive approach allows for a thorough examination of the impact of missing data on our study outcomes.

In the second approach, we are aware that throughout the trial, some participants may leave the study due to a high number of exacerbations or death before reaching their 48-week follow-up. This leads to missing data that is not at random, rendering

standard imputation methods inappropriate. Therefore, the data for key secondary outcomes for these participants will be analysed in the following way:

Pattern Mixture Model:

Robustness of the results will be assessed within the pattern mixture model. A pattern mixture model is a type of statistical model used to analyse data with missing values, especially when the missingness is not at random (MNAR).

This method is a 2-stage procedure where the 1st stage involves the use of multiple imputation to impute all missing values assuming data are “missing at random”.

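### The protocol limits the two count outcomes to patients with 24 weeks of treatment, and the SAP drops that rule unrecorded while contradicting itself on complete-case analysis

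*Protocol*

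**What the plan says.** **Protocol.** Section 10.3.3 opens with a general rule: "All secondary end-points will be analysed using the ITT population, with the exception of adverse events". It then makes an exception for the readmission and moderate-exacerbation counts, where "patients will be included in the analysis if they have a received a minimum duration of trial treatment of 24 weeks". Section 10.7 has the same pair. It promises intention to treat for each efficacy outcome, dosed or not, and then states that "number of hospital readmissions and number of moderate exacerbations over 48 weeks, will be analysed on the per-protocol population", with the same 24-week condition. The endpoint table in 3.5 repeats the 24-week treatment minimum for both counts. For those randomised from July to December 2023, section 4.1 says "Participants will be dosed for a minimum of 20 weeks", which is six doses from week 0 to week 20.

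**SAP.** Section 6.5.1 states: "All secondary outcome (except for AEs and SAEs) will be analysed on the modified intention to treat population". Section 4.3 defines that population so that "participants with missing outcome data will be excluded from the analysis (i.e complete case analysis". The first paragraph of 6.5.3, which repeats Protocol 10.8, also prescribes complete-case analysis for count outcomes. Yet the section written for the counts, 6.5.1.3, fits a negative binomial model with a log-time offset in which "all of the available observed data are analysed without deletion nor imputation". Sections 4.4 and 6.5.2 add a per-protocol analysis as secondary. That population is defined by the absence of a major deviation and has no 24-week condition. Section 6.8 gives the changes to the planned analysis as none.

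**The concern.** Whether a patient reaches 24 weeks of treatment is settled after randomisation and is related to outcome. Those who die early, stop because they are unwell, or are never dosed are left out. The remaining groups are no longer those that randomisation created, and the comparison can shift either way if the arms lose patients differently. SAP 6.5.3 itself expects some participants to leave because of frequent exacerbations or death, and calls the resulting data not missing at random.

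The two counts are among the three outcomes that SAP 6.5.3 treats as key secondary outcomes, and readmission is the subject of the trial. Much of the excluded information is due to be collected. Protocol 7.8 asks those who stop treatment to let admissions and deaths still be recorded, and 7.11 follows those lost through hospital records.

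The SAP's complete-case wording raises a related difficulty. Deleting people with partial follow-up is not generally valid under the missing-at-random assumption offered to justify it, whereas a likelihood model on all observed person-time can be.

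**Working it through.** **1. The plan's own figure.** The documents give no sample size or power for the counts. The primary-outcome size does reproduce. With HR 0.6, two-sided 5% and 80% power, Freedman's formula gives 7.849 × (1.6/0.4)² = 125.6, so 126 events. Event probabilities are 0.65 (control) and 1 − 0.35^0.6 = 0.467 (active), mean 0.559. Then 126/0.559 gives 226, and 226/0.95 gives 238. This point does not affect it.

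**2. The rules for the counts side by side.**

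| Source | Population | Early deaths and stoppers |
|---|---|---|
| Protocol 10.3.3 (opening), 10.7 (opening) | All randomised | Kept |
| Protocol 10.3.3, 10.7, table 3.5 | At least 24 weeks of treatment | Removed |
| SAP 6.5.1 with 4.3 and 6.5.3 (first paragraph) | Modified ITT, complete case | Removed if a partial count is 'missing' |
| SAP 6.5.1.3 | All observed data, log-time offset | Kept |
| SAP 4.4 and 6.5.2 (secondary) | No major deviation | Kept with shortened time, unless stopped for non-compliance |

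The first two rows conflict within the protocol. The third and fourth conflict within the SAP. The fifth does not compete with them, because the SAP labels it secondary. It has its own gap: a participant who was never dosed has no treatment time, so the log treatment-time offset is undefined.

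**3. The 24-week rule against the truncated schedule.** For the December 2023 entrants, follow-up is 24 weeks, the last dose is at week 20, and there are 20/4 + 1 = 6 doses.

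- Last minus first dose (SAP 6.3): 20 weeks, which fails.
- Last dose plus 4 weeks (SAP 4.4): 24 weeks, which just passes. If the last dose moves by its ±7-day window, this is 23 to 25.

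The November cohort (last dose at week 24) passes on either measure. The protocol does not say which measure applies.

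**4. How many the 24-week rule could remove.** Excluded = 238 × [1 − 0.95 × (1 − d) × (1 − s)]. The 0.95 is the protocol's own 5% never dosed, which alone is about 12 of 238. The early-death proportion d and other stopping s are assumptions, because the documents give neither by week 24.

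- d = 3%, s = 0: 238 × 0.079 = 19 (8%).
- d = 6%, s = 10%: 238 × 0.196 = 47 (20%).
- d = 12%, s = 20%: 238 × 0.331 = 79 (33%).

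Exclusions of December entrants would be additional.

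**5. What selection can do to the rate ratio.** This is a simulation in which every input is assumed: 1.5 readmissions per 48 weeks in control, gamma frailty variance 0.8, a death hazard of 0.15 per 48 weeks scaled by frailty, and a stopping hazard of 0.3 or 0.6 per 48 weeks scaled by each patient's readmission rate. In the active arm both hazards also scale with the treatment rate ratio. Follow-up for readmissions continues after stopping. The last column drops everyone who died or stopped before week 47, an outer case, because stopping treatment is not leaving the trial.

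| True ratio; stopping hazard control/active | All randomised | 24-week rule | 47-week complete case |
|---|---|---|---|
| 1.0; 0.3/0.3 | 1.00 | 1.00 | 1.00 |
| 1.0; 0.6/0.3 | 1.00 | 1.10 | 1.18 |
| 1.0; 0.3/0.6 | 1.00 | 0.91 | 0.85 |
| 0.6; 0.3/0.3 | 0.61 | 0.64 | 0.67 |
| 0.6; 0.6/0.3 | 0.61 | 0.71 | 0.79 |
| 0.6; 0.3/0.6 | 0.61 | 0.60 | 0.60 |

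With no effect and equal stopping there is no bias. With unequal stopping its sign follows the arm that loses more patients.

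A different set of assumptions gives a smaller answer. Take 1.4 events a year, the same frailty variance, exit that also ends follow-up in about 19% of controls before week 24, and an exit hazard ratio of 0.6. A true ratio of 1.00 then reads 1.07 under a 24-week cut (applied to follow-up) and 1.05 with all randomised. A true 0.70 reads 0.75 and 0.73. Removing the cut changes the answer by about 0.02.

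**The case against.** The best defence is that Protocol 10.3 leaves full analysis detail to the SAP. The SAP has abandoned the 24-week rule, ranks its per-protocol analysis as secondary, and already contains the right model in 6.5.1.3. For early leavers, 6.5.3 also plans pattern-mixture analyses of these very counts. The affected outcomes are secondary ones in a Phase IIb trial. All of that stands, and it limits the severity.

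Three stronger readings are tempting, and the documents do not support them.

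- A reader might infer that the SAP's primary count analysis certainly removes early deaths and dropouts, since "Individuals will be considered to have had some missing data for the two count variables if they have less than 47 weeks" and SAP 4.3 excludes missing outcomes. But that definition sits among the sensitivity analyses, where it sets up the imputation, and nowhere says such people leave the primary count analysis. A footnote in 6.5.3 keeps their observed counts. A partial count with known exposure need not be a missing outcome. The exclusion is possible, not established.
- A reader might infer that fully compliant December 2023 entrants are definitely excluded by the protocol. That holds on the SAP 6.3 adherence measure but not on the SAP 4.4 measure.
- A reader might infer that the analyst has a free choice among equal answers. The SAP's ranking of primary over secondary rules this out for per-protocol. What remains open is complete case against all observed data.

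The defence does not remove the conflict within the protocol, the contradiction between SAP 4.3 or 6.5.3 and 6.5.1.3, or the entry of no changes in SAP 6.8 when the population for two outcomes has changed.

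**Conclusion.** The point holds for the protocol's 24-week rule, which selects after randomisation, contradicts the intention-to-treat sentences beside it, and leaves the last-entry cohort excluded or borderline. It also holds for the SAP, which departs from the protocol without recording it and gives two incompatible instructions for the primary count analysis. Whether the SAP would in practice drop early deaths and dropouts is ambiguous, and its analyses for data not missing at random are a partial safeguard.

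The 8% to 33% exclusion range and the simulated ratios rest on assumed death, stopping and frailty inputs. They show that bias in either direction is possible, from about 0.02 upward in the scenarios where the arms lose patients unequally, and do not predict it. The primary outcome, analysed on all randomised participants with censoring, is untouched. This is a should-fix, best settled before database lock because the trial statistician has access to allocation (Protocol 7.4).

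**What to change.** - **Protocol 10.3.3, 10.7 and table 3.5:** delete the 24-week treatment condition for the two counts.
- **SAP 4.3, 6.5.1 and 6.5.3:** state that the complete-case exclusion does not apply to the counts, and that participants with under 47 weeks of follow-up stay in the primary count analysis.
- **SAP 6.5.1.3:** define the primary count analysis as all randomised participants with any follow-up, by allocated arm, with log follow-up time as offset. Follow-up time should be the period over which that outcome was actually ascertained. For moderate exacerbations this may be shorter than for admissions, because the minimum data after stopping treatment in Protocol 7.8 are admissions and deaths.
- **SAP 4.4 and 6.5.2:** keep the per-protocol analysis as supportive only, restricted to participants with at least one dose so that the log treatment-time offset exists.
- **SAP 6.8:** record the departure from the protocol population and the reason.

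The cost is wording in the SAP and a matching protocol amendment or note. No new data or model is needed, since the offset model and continued data collection are already planned.

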10.3.4 Exploratory outcome analysis

All exploratory outcomes will be analysed using appropriate statistical tests according to the nature of the variables. No formal hypotheses testing will be performed.

10.4 Subgroup analyses

Subgroup analyses of the primary outcome will be carried out on the stratification factors: MRC dyspnoea score (≤ 3 , > 3) and past hospitalisation in the previous 12 months (0 , ≥ 1) and WHO clinical progression score at baseline (4, 5, 6). A stratified Cox model will be fitted to allow the form of the underlying hazard function to vary across the levels of prognostic variables.

10.5 Adjusted analysis

Modelling of the primary and all secondary outcomes will be adjusted for the baseline MRC dyspnoea score (≤ 3 , > 3) and past hospitalisation in the previous 12 months (0 , ≥ 1), used as a stratification factor at randomisation.

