10 STATISTICS AND DATA ANALYSIS

10.1 Sample size calculation

Readmission rates at 6, 9 and 12 months were 51%, 59% and 64% respectively for patients admitted with a diagnosis of COPD (ICD code: J44) in Leicestershire in 2015. This is in line with national data from the HQIP RCP National COPD audit (2014) which had a readmission rate of 43% at 3 months. In addition, 6% of patients discharged from hospital with an exacerbation of COPD died in the 12 months following admission without hospital readmission.

National UK data from the HQIP funded RCP/BTS National COPD audit (2014; data unpublished) showed 24.9% patients had an eosinophil count of ≥ 300 cells/ μL on admission. In patients with an eosinophil of ≥ 300 cells/ μL on admission ($n=1,587$), 46.1% of patients were readmitted within 3 months of initial hospitalisation, similar to the non-eosinophilic COPD population.

Assuming 65% of patients receiving usual care will have an event by 48 weeks (composite endpoint: hospitalisation or death) and those treated with mepolizumab have a hazard ratio of 0.6, then 226 patients (113 per group) would be required to show a statistical difference power 0.8, $\alpha=0.05$). We have also assumed 5% drop-out (recruited but not receiving first dose) and therefore the final recruitment target of 238 patients.

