6.4 Primary Outcome Analysis

6.4.1 Primary Analysis of Primary Outcomes

The primary analysis will take place on the intention to treat population. All participants will be included in the model using censored values for participants not experiencing an event during their follow-up period.

The primary analysis will fit the Cox proportional hazard model for the primary outcome of the time to re-hospitalisation or death (any cause) as the dependent variable, treatment group as an explanatory factor and baseline MRC dyspnoea score (≤ 3 , > 3) and past hospitalisation in the previous 12 months ($(0, \geq 1)$) (Stratification factors). This analysis will be accompanied by Kaplan-Meier survival curves alongside with log rank test to compare the survival rate between the two groups. A hazard ratio (HR) of the mepolizumab relative to placebo, with their associated two-sided 95% confidence interval and p-values will be reported. A p-value ≤ 0.05 will be considered as significant difference.

Time until event (re-hospitalisation or death from any cause) will be measured in days from randomisation until re-hospitalisation, death or 12-month follow-up assessment, whichever happens first. Participants with no event (no re-hospitalisation or alive) assessed during follow-up visits will be censored at the last assessment date free from event.

Participants who do not complete the 12-month follow-up will be included in the primary analysis; those without a recorded event will be censored. Participants who withdraw from the trial will be censored at the date of withdrawal and participants lost to follow up will be censored at the date last assessment.

Proportional hazard assumption for the Cox proportional hazard model will be checked using the statistical tests and graphical diagnostics based on the Schoenfeld residuals.

Where participants don't reach the 12 month assessment but do not experience an event the last date of assessment known to be event-free will be used as the censor

value (right censoring). This will apply to participants who are withdrawn and/or lost to follow-up for any reason or receive truncated follow-up as part of the revised protocol. In the event of encountering multiple events occurring at the same time t , Efron's method for dealing with tied survival times will be implemented when fitting the Cox model to the data.

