	Min, Max
Number of courses of antibiotics without steroids for your chest (COPD exacerbations) in previous 12 months	N
	Mean [SD]
	Median [IQR]
	Min, Max
Number of courses of both antibiotics and steroids for your chest (COPD exacerbations) in previous 12 months	N
	Mean [SD]
	Median [IQR]
	Min, Max
Systolic (mmHg)	N
	Mean [SD]
Pre-Dose	Median [IQR]
	Min, Max
Diastolic (mmHg)	N
	Mean [SD]
Pre-Dose	Median [IQR]
	Min, Max
Heart rate (bpm)	N
	Mean [SD]
Pre-Dose	Median [IQR]
	Min, Max
Temperature (°C)	N
	Mean [SD]

Pre-Dose	Median [IQR]
	Min, Max
SpO ₂ (%)	N
	Mean [SD]
Pre-Dose	Median [IQR]
	Min, Max
Respiratory rate (per min)	N
	Mean [SD]
Pre-Dose	Median [IQR]
	Min, Max
Systolic (mmHg)	N
	Mean [SD]
Post-Dose	Median [IQR]
	Min, Max
Diastolic (mmHg)	N
	Mean [SD]
Post-Dose	Median [IQR]
	Min, Max
Heart rate (bpm)	N
	Mean [SD]
Post-Dose	Median [IQR]
	Min, Max
Temperature (°C)	N
	Mean [SD]
Post-Dose	Median [IQR]
	Min, Max
SpO ₂ (%)	N
	Mean [SD]
Post-Dose	Median [IQR]
	Min, Max
Respiratory rate (per min)	N
	Mean [SD]
Post-Dose	Median [IQR]
	Min, Max
eMRC dyspnoea score (stable state)	
2: Breathless when hurrying on the level or walking up a slight hill
 
3: Walks slower than peers or stops when walking on the flat at own pace
 
4: Stops after walking 100m, or for a few minutes, on the level
 
5A: Too breathless to leave the house & independent in washing and/or dressing

	5B: Too breathless to leave the house & dependent in washing and dressing
	Missing*
WHO: Highest level of intervention during baseline admission	No oxygen therapy
	Oxygen by mask or nasal prongs
	Oxygen by NIV or high flow
Time to discharge from index admission (days)	N
	Mean [SD]
	Median [IQR]
	Min, Max
*FEV1, litre	N
	Mean [SD]
	Median [IQR]
	Min, Max
*FEV1, %	N
	Mean [SD]
	Median [IQR]
	Min, Max
*FVC, litre	N
	Mean [SD]
	Median [IQR]
	Min, Max
*FVC, %	N
	Mean [SD]
	Median [IQR]
	Min, Max
*FEV1/FVC ratio, %	N
	Mean [SD]
	Median [IQR]
	Min, Max

Abbreviations: SD= Standard deviation; IQR= Inter-quartile range, Min=Minimum; Max=Maximum; N= number of observations

Data are n (%), mean (SD), or median (IQR), unless otherwise stated.

Figure 2: Proportion of patients in each dose

Figure 3: Number of doses per patient

Figure 4: Kaplan-Meier survival curves of the primary outcome by randomised group

Table 4: Primary Analysis of Primary Outcome: the time from randomisation to next hospital readmission or death (all cause)

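### The primary Cox model is valid but adjusts only for two dichotomies; adding age and the graded eMRC score, both already collected, could gain about 0 to 4 points of power at little cost.

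*Protocol*

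**What the plan says.** **Model.** Protocol 10.3.2: "The primary analysis will fit the Cox proportional hazard model for the primary outcome", with treatment, dyspnoea score (≤3, >3) and past hospitalisation in the previous 12 months (0, ≥1). Protocol 10.5 generalises this: "Modelling of the primary and all secondary outcomes will be adjusted for the baseline MRC dyspnoea score" and for past hospitalisation. SAP 6.4.1 repeats the model, and SAP 6.7 specifies the stable-state eMRC score. These are the two factors used to stratify randomisation (Protocol 7.3).

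**What is collected.** Age heads the baseline list in Protocol 10.3.1. Two eMRC scores, current and stable, are taken at visit 1 (Protocol Appendix 1). In SAP Appendix 1, Table 2, the row "eMRC dyspnoea score (stable state") lists grades 2, 3, 4, 5A and 5B, plus a line for missing values.

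**What is not planned.** No other covariate-adjusted analysis of the primary outcome is specified, and SAP 6.4.3 plans no sensitivity analysis of it. SAP 6.4.1 asks for a martingale residual plot to check continuous covariates, but the model has none.

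**Design target.** Protocol 10.1: "Assuming 65% of patients receiving usual care will have an event by 48 weeks", "those treated with mepolizumab have a hazard ratio of 0.6", "then 226 patients (113 per group) would be required", at power 0.8 and alpha 0.05.

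**The concern.** Cutting eMRC at 3 treats grade 2 like grade 3, and grade 4 like 5b. Yet the plan regards dyspnoea as prognostic. It stratifies on it, Protocol 10.4 calls the stratified-model variables prognostic, and the SAP's eMRC definition cites a study whose title names dyspnoea severity as a predictor of in-hospital mortality and early readmission. Age does not enter the model at all.

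In a Cox model, leaving out a prognostic covariate pulls the estimated treatment hazard ratio towards 1 and lowers power. The design has little in reserve: it targets 80% on events by 48 weeks, while participants randomised from July to December 2023 are followed for less time (Protocol 4.1). What is at stake is some power that could be recovered from data already held. The validity of the test is not in question.

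**Working it through.** **1. Reproduce the sample size.** Inputs from Protocol 10.1: control risk 65%, HR 0.6, power 0.8, alpha 0.05. SAP 6.4.1 makes the test two-sided: "with their associated two-sided 95% confidence interval and p-values will be reported".

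- Freedman events: ((1 + 0.6)/(1 − 0.6))² × (1.960 + 0.842)² = 16 × 7.85 ≈ 126.
- Treated risk: 1 − 0.35^0.6 = 46.7%. Average risk: (65 + 46.7)/2 = 55.9%.
- N = 126/0.5587 = 225.5, so 226. With 5% drop-out: 226/0.95 = 237.9, so 238.

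Both figures match the plan. (The Schoenfeld formula would give 121 events and N = 217.)

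**2. Gain in terms of explained variation.** Let R² be the outcome variation explained beyond the two dichotomies. As an approximation, information is multiplied by 1/(1 − R²), so power = Φ(2.802/√(1 − R²) − 1.960).

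| Added R² | Power |
|---|---|
| 0 | 80.0% |
| 1% | 80.4% |
| 2.5% | 81.0% |
| 5% | 82.0% |
| 10% | 84.0% |

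A gain of 1 to 4 points thus needs an added R² of about 2.5% to 10%. That is worth 226/0.975 − 226 ≈ 6 to 226/0.90 − 226 ≈ 25 extra patients.

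**3. Simulated Cox models, full 48-week follow-up.** N = 226, 65% control risk, HR given the two dichotomies about 0.6, 3,500 trials per row. Assumed, not in the documents: grade mix 15/30/30/15/10%, 60% with a prior admission, prior-admission HR 1.5. The extended model keeps both stratification terms and adds linear age and the graded score. Changes are computed before rounding.

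| HR per SD of age | HR per eMRC grade | Planned model | Extended model | Change (points) |
|---|---|---|---|---|
| 1.0 | 1.0 | 81.5% | 81.3% | −0.2 |
| 1.1 | 1.1 | 81.3% | 81.3% | −0.1 |
| 1.15 | 1.2 | 80.3% | 80.6% | +0.3 |
| 1.2 | 1.3 | 80.0% | 82.2% | +2.2 |
| 1.3 | 1.4 | 81.0% | 83.9% | +2.9 |

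One power estimate has a standard error of √(0.8 × 0.2/3,500) ≈ 0.7 points, so the first three rows show no clear gain.

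**4. Simulation with truncated follow-up.** 238 patients, one sixth followed for 24 to 44 weeks. Assumed: grade mix 15/25/30/20/10%, age SD 9 years, log-HR for past hospitalisation 0.4 with prevalence 55%. Linear log-HRs per eMRC grade / per 10 years of age ran from 0/0 through 0.2/0.1 and 0.3/0.2 to 0.4/0.3.

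- *Adding* age and grade to both stratification terms: about +0.3, +0.8, +1.8 and +3.9 points. The +0.3 with no prognostic effect is simulation noise.
- *Replacing* the eMRC cut with the grade, plus age: 82.2% to 82.1%, 80.6% to 81.5%, 79.8% to 81.9%, and 78.6% to 83.1%.

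**5. If the true eMRC effect is a step at the cut and age has no effect.**

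- *Replacing* the cut loses power: −0.3, −0.9 and −1.6 points at step log-HRs of 0.4, 0.7 and 1.0 (4,000 runs). A separate run at 1.0 gave 83.3% to 80.9%, or −2.4 points.
- *Adding* the grade while keeping the cut costs at most 0.4 points, within simulation error.

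**6. Type I error.** The planned and extended models gave rates of 5.0% and 5.4% between them, so neither departs materially from 5%.

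**The case against.** The strongest case against is that nothing is wrong. The planned model is pre-specified, consistent across both documents, and adjusts for exactly the factors used in randomisation. That stands. A reader might infer bias or an inflated type I error; the documents support neither.

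A reader might also infer a definite loss of 1 to 4 points. The documents give no prognostic strength for age or for eMRC within each half of the cut, and nothing in them calls age prognostic. The cited dyspnoea study supports the idea only through its title. With weak effects the gain is nil.

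Nor do the documents support replacing the eMRC cut. If the effect is a step at the cut, replacement lowers power (step 5 of the working). Keeping the cut removes this objection.

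The grade is also less secure than the stratum. The stratum must be entered to randomise (Protocol 7.3.1), whereas SAP 3.2.1 has the analysis value captured after randomisation. The SAP table allows for missing grades, and the plan expects 5% never to be dosed. Dropping those with a missing grade would lose information at about the rate gained: 2.5% missing cancels an added R² of 2.5%. This stands, so a missing-grade rule is needed.

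The baseline adjustment in SAP 6.5.1.2 is no evidence of inconsistency. There each longitudinal outcome is adjusted for its own baseline value, which a time-to-event outcome does not have.

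Last, the change would come late. Randomisation was due to end in December 2023, and the trial statistician has access to the allocations (Protocol 7.4). This restricts how the covariates may be chosen, but it does not rule out an amendment.

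**Conclusion.** The point holds as a cheap improvement. The primary analysis is valid, but it leaves unused two baseline variables that are already collected. With both stratification terms kept and age and the graded eMRC score added, the expected change in power is about 0 to 4 points:

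- essentially none if the covariates are weak (HR up to about 1.15 per SD of age and 1.2 per grade), or if eMRC acts only as a step at the cut;
- about 2 to 4 points if they are moderately to strongly prognostic.

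These sizes rest on assumed prognostic strengths, grade mix and prior-admission effect, and on exponential or similarly simple event times. The direction does not depend on fine detail: no setting showed a loss beyond simulation error for the extended model. The gain should not be called certain or free. The hazard ratio becomes conditional on more covariates (in simulation, from 0.60 to about 0.59), and a missing-grade rule and a timely amendment are needed.

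**What to change.** In Protocol 10.3.2 and 10.5 and SAP 6.4.1 and 6.7:

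1. Keep eMRC (≤3, >3) and past hospitalisation (0, ≥1) as randomised.
2. Add age as a linear term and the stable-state eMRC grade as an ordered score (2, 3, 4, 5a, 5b).
3. If the grade is missing, use the median grade of the participant's randomisation stratum, taken over both arms together, so that no ITT participant is dropped.
4. In SAP 6.4.3, add the stratification-factor-only model as a sensitivity analysis.
5. State whether the added terms carry over to the secondary time-to-event outcomes, because SAP 6.5.1.1 ties them to the primary method.
6. Justify the covariates from prior knowledge, not from trial data, and record this in a dated SAP amendment before database lock. The SAP introduction allows amendment up to that point.

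The cost is wording, two extra model terms and one simple imputation rule. No new data are needed, and the martingale residual plot already listed in SAP 6.4.1 would then have covariates to check. If the database is already locked or the data unblinded, leave the primary model as it is and report the extended model as supplementary.
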